3. STUDY DESIGN

3.1 Overview of study design

This is a non-randomized, open-label, Phase Ib study to assess the safety and efficacy of oral decitabine (ASTX727) and durvalumab (MEDI4736) combination therapy in the treatment of patients with recurrent and/or metastatic squamous cell carcinoma of the head and neck (SCCHN) who have progressed during or after treatment with anti-PD-1, anti-PD-L1, and/or anti-CTLA-4 for recurrent and/or metastatic disease. The primary endpoint is to determine the BED of oral decitabine (ASTX727) in combination with durvalumab (MEDI4736) therapy. The secondary endpoint is to assess the safety of oral decitabine (ASTX727) in combination with durvalumab (MEDI4736) therapy.

The trial opened with the use of subcutaneous (SC) injection of azacitidine. All patients received azacitidine SC injection on either Days 1-5 alone or Days 1-5 and 8-12 in a 4-week cycle, durvalumab (MEDI4736) 1500 mg via intravenous (IV) infusion every 4 weeks (q4w), and tremelimumab 75 mg via IV infusion q4w. Azacitidine was administered alone in Cycle 1 and the combination of azacitidine, durvalumab, and tremelimumab therapy was started in Cycle 2. Dose Limiting Toxicity (DLT) was assessed through 28 days post Cycle 2. After cycle 2, patients continued with azacitidine, durvalumab and tremelimumab combination therapy for Cycles 3-5 and azacitidine and durvalumab for Cycles 6-12 or until confirmed PD, initiation of alternative cancer therapy, unacceptable toxicity, withdrawal of consent, or another discontinuation criterion is met, whichever occured first. However, treatment consisting of 5 to 10 daily visits for a large-volume SC injection continuing for several months or even years, represented a significant hardship for patients with possible consequences of non-compliance or earlier discontinuation of a beneficial treatment. Therefore, an oral DNA methyltransferase inhibitor is being evaluated to ease the burden of daily visits for those patients who are benefitting the most and need continuing treatment for long periods. Furthermore, since the oral DNA methyltransferase inhibitor is investigational, we plan to combine it with the FDA approved durvalumab.

Therefore, all patients enrolled with or after protocol version 11.0 will receive an oral tablet of ASTX727 (35 mg decitabine/100 mg cedazuridine) daily on either Days 1-3, Days 1-4, or Days 1-5 and durvalumab (MEDI4736) 1500 mg via IV infusion x 1 in a 4-week cycle. Oral

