6.3.1 Definition of BED

Biologically effective dose (BED) is defined as the dose of oral decitabine (ASTX727) that results in at least a 10% decrease in LINE-1 methylation level from the baseline sample to the 8 week post baseline tumor sample in at least 50% of patients treated within a dose level. As LINE-1 (long interspersed element-1) is a repetitive DNA retrotransposon that duplicates via a copy-and-paste genetic mechanism. As LINE-1 constitutes approximately 17% of the human genome, the extent of LINE-1 methylation is regarded as a surrogate marker of global DNA methylation. ASTX Pharmaceuticals has assessed changes in LINE-1 methylation with ASTX727 as a marker of efficacy in their prior clinical trials. The change in LINE-1 methylation is a working rule and a panel of markers will be assessed and the dose with the most viable panel and lowest adverse event profile will be used in the expansion cohort of the study.

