11 STATISTICAL METHODS AND SAMPLE SIZE DETERMINATION

Rational for Changes from SC Injection to Oral Drug

This trial opened with use of subcutaneous (SC) injection of azacitidine. Treatment, ie, 5 to 10 daily visits for a large-volume subcutaneous injection continuing for several months or even years, represents a significant hardship for patients. A possible consequence is non-compliance or earlier discontinuation of a beneficial treatment. Successful development of an oral DNA methyltransferase inhibitor will ease the burden of long-duration SC therapy, particularly for those patients who are benefitting the most and need continuing treatment for long periods.

The primary objective and design and number of doses to be tested with oral decitabine remain the same as in the original protocol which used SC injection of azacitidine. The overall sample size has been revised to account for accrual of patients who receive oral decitabine in addition to the patients accrued when the original protocol opened using SC injection of azacitidine.

The primary objective of the phase I trial is to determine the BED. The BED is to be determined among evaluable patients (eligible patients who at least begin protocol treatment and have an evaluable pre- and on-treatment (8-week) biopsy sample available). Three doses of oral decitabine (ASTX727) are scheduled to be tested. BED is defined as the dose of oral decitabine (ASTX727) that results in at least a 10% decrease in LINE-1 methylation from the baseline biopsy to the 8-week on-treatment tumor biopsy in at least 50% of patients treated within the same dose level. If the BED has not been determined in the first 2 dose levels and it is safe to do so, then the study will re-open to accrual and a subsequent group of 3 patients will receive the $3^{\rm rd}$ dose level. IF both the first 2 dose levels result in \geq 10% decrease in LINE-1 methylation, then the dose which induces the greatest fold change in HLA Class I/II APM expression and/or CD8+ T cell infiltration and with the lower adverse event profile will be the dose utilized for the dose expansion cohort. The change is a working rule and a panel of markers will be assessed and the dose with the most viable panel and lowest adverse event profile will be used in the expansion cohort.

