Although assessment of the BED is primary, the dose also needs to be safe. Each dose will also be assessed for safety. Six patients will be entered into dose level 1. Adverse events (i.e. dose limiting toxicity (DLT) assessment as defined in section 6.4) will be assessed through 28 days post cycle 2. If two or more of the first six subjects experience a DLT, then the dose will be reduced and an additional six patients will be treated at the reduced dose. If two or more of the six at the reduced dose experience a DLT, then the study will be terminated. If at any time during accrual to a dose cohort, 2 or more patients in a dose cohort experience DLT, enrollment to that dose cohort will be terminated. If less than two of the six patients treated at dose level 1 experience a DLT, a subsequent group of six patients will receive dose level 2.

Drug Substance Azacitidine/Decitabine (ASTX727)

Study Code 15-11430

Edition Number 13.0

Date 09202024

Accrual will be suspended until review of the BED rate in tissue from baseline and 8 weeks post baseline has been completed from patients entered into the first 2 dose levels. If the BED has not been determined in the first 2 dose levels and it is safe to do so, then the study will re-open to accrual and a subsequent group of 6 patients will receive the 3rd dose level. Once the BED is determined, dose escalation will stop and the BED will be used in the expansion cohort.

Approximately 28 evaluable patients (eligible patients who at least begin protocol treatment and have an evaluable pre- and on-treatment (8-week) biopsy sample available) are estimated to be accrued during the BED assessment phase with the oral decitabine. This is based on studying 6 evaluable patients per dose level with a total of 3 dose levelsand an additional 10 evaluable patients entered at the BED ('expansion cohort' accrued to ensure that the BED rate is acceptable). The further assessment of the BED will be based on studying these 10 additional patients. Additional subjects may be enrolled into the cohort(s) to ensure that the required number of evaluable pre- and on-treatment biopsy samples are available to adequately determine the BED. See end of this statistical section for overall sample size.

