BED is defined as outlined above. Six evaluable patients are estimated to be accrued per dose level with the additional 10 evaluable patients in the expansion cohort. The below table gives the probabilities of observing at least 33% of patients within a dose level with the BED for the first 6 patients for varying true rates of the BED.

True BED rate	Probability of ≥2 out of 6 patients in a dose level meet BED definition.	Probability of ≥7 out of 16 meet BED definition (given that ≥2 out of 6 patients in the dose level from original testing meet the BED definition plus the expansion cohort)
50%	.89	.73
55%	.93	.84
60%	.96	.92

For example, if the true rate of BED is 50%, the probability of observing ≥ 2 out of 6 patients in a dose level with the BED is 89%. The above table also shows the probabilities of successfully declaring the BED after cohort expansion (the additional 10 patients to a dose level) (last column). With 6 patients entered in a dose level and 10 in the expansion cohort (with cutpoints as in the above table), if the true BED rate were instead as low as 27%, the probability of a dose level being used as the BED in the phase II portion of this trial is only 10%.

With an estimated monthly accrual of 2 patients, accrual with use of the oral agent is estimated to complete in approximately 9 months. As of October 1, 2019, n=11 patients have been registered

Drug Substance Azacitidine/Decitabine (ASTX727)

Study Code 15-11430

Edition Number 13.0

Date 09202024

to receive SC injection of azacitidine. Accrual for patients to receive SC injection of azacitidine continues during review and approval of this amendment to change to administration of oral decitabine. With approximately 2-3 more patients enrolled to receive SC injection of azacitidine during amendment review, a total of up to N=41 (13 SC injection of azacitidine + up to 28 oral decitabine) patients could be entered.

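### Two rules choose the expansion dose: one expands the LINE-1-defined BED, the other a dose picked on an undefined marker panel that need not have met the BED definition

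*Combined protocol and SAP*

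**What the plan says.** Section 3.1 sets the aim: "The primary endpoint is to determine the BED of oral decitabine (ASTX727) in combination with durvalumab (MEDI4736) therapy". Section 11 defines the BED as the dose giving "at least a 10% decrease in LINE-1 methylation from the baseline biopsy to the 8-week on-treatment tumor biopsy in at least 50% of patients" at that dose level. Sections 3.1, 6.2 and 6.3.1 give the same definition.

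**Rule A, expand the BED.** Section 11: "Once the BED is determined, dose escalation will stop and the BED will be used in the expansion cohort". Section 3.1 has the same sentence, and Section 6.1.2 expands the group in which the BED was found. Section 11 counts 10 further evaluable patients at the BED and gives their purpose as making sure that the BED rate is acceptable.

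**Tie-break within Rule A.** If both of the first two levels qualify, Sections 3.1, 6.2 and 11 choose between them on HLA Class I/II APM expression and/or CD8+ infiltration, together with the adverse event profile.

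**Rule B, expand the panel's choice.** Section 6.3.1: "The change in LINE-1 methylation is a working rule and a panel of markers will be assessed", and then "the dose with the most viable panel and lowest adverse event profile will be used in the expansion cohort of the study". Section 11 repeats this: "The change is a working rule and a panel of markers will be assessed and the dose with the most viable panel" and the lowest adverse event profile goes to expansion.

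**The concern.** Both rules are current, operative text, and they can name different doses. Rule A makes the LINE-1 result binding. Rule B calls it provisional and hands the choice to a panel, without limiting the panel to levels that passed LINE-1.

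Rule B also cannot be applied reproducibly. No section says which markers form the panel, what makes a panel viable, or how the markers are weighted. Section 8.3.1 gives an open-ended list of further immune markers but does not call it the decision panel. Rule B needs a single dose to be best on the panel and lowest on adverse events, and gives no instruction if these are two different doses. The choice would be made after biopsy and safety data are seen, in an open-label study with six patients per level.

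At stake is whether the expansion cohort tests the dose that met the primary definition, and whether the operating characteristics in Section 11 apply to the dose that is expanded.

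**Working it through.** **1. Where the rules diverge.**

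| Outcome at the first two levels | Rule A | Rule B |
|---|---|---|
| One level meets LINE-1 | That level is expanded | Either level could be |
| Both meet LINE-1 | HLA/CD8 and adverse event tie-break | Panel and adverse events |
| Neither meets LINE-1 | Go to level 3 if safe | No condition stated |

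The first row is not rare. As an illustration, assume independent levels with true rates of 27% and 50%. The chances of at least 3 of 6 are .2023 and .6562. Exactly one level qualifies with probability .2023 × .3438 + .6562 × .7977 = .0695 + .5235 = .593.

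**2. Reproducing Section 11.** Inputs from its table and text: 6 patients per level, 10 in expansion, cuts of at least 2 of 6 and at least 7 of 16, true rates of 50%, 55%, 60% and 27%.

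First stage: P(X ≥ 2), X ~ Bin(6, p).
- 50%: 1 − (.0156 + .0938) = .8906 (plan .89)
- 55%: 1 − (.0083 + .0609) = .9308 (plan .93)
- 60%: 1 − (.0041 + .0369) = .9590 (plan .96)

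Both stages: sum over x = 2 to 6 of P(X = x) × P(Y ≥ 7 − x), Y ~ Bin(10, p).
- 50%: .1460 + .2588 + .2216 + .0927 + .0156 = .7347 (plan .73)
- 55%: .843 (plan .84)
- 60%: .917 (plan .92)
- 27%: .0322 + .0417 + .0227 + .0050 + .0004 = .1020 (plan 10%)

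Every stated figure is reproduced, as the joint probability of passing LINE-1 in the first 6 and then reaching 7 of 16. That is Rule A with a 2-of-6 gate.

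**3. Removing the LINE-1 gate.** Suppose the panel sends a level to expansion whatever its first-stage count, and only 7 of 16 is required. The sum then also takes in x = 0 and x = 1.
- 27%: .1020 + .0009 + .0096 = .1125, or .112 unrounded (.11249)
- 50%, 55%, 60%: .773, .876, .942

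The .102 includes the chance of reaching expansion, while the .112 takes expansion as given. The chance that the panel picks a given level cannot be calculated, because the panel has no criterion.

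A 27% level that has shown only 0 or 1 of 6 has (.0009 + .0096) / .4872 = .022 chance of reaching 7 of 16. Ten patients placed there would rarely lead to a declared BED.

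**4. With the gate read from the 50% definition** (at least 3 of 6), the joint figure at 27% is .070. The difference from .112 is then about four points rather than one.

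**The case against.** The strongest reply is that the panel sentence only elaborates the tie-break. In Section 11 it follows the rule for two qualifying levels and has the same form: markers plus adverse events, then expansion. LINE-1 still governs the other steps. Accrual stops for its review, level 3 opens only if no BED has been found, and escalation stops once one has. This reading is possible in Section 11. Section 6.3.1 does not support it: there the sentence names LINE-1, follows the BED definition directly, and no tie-break appears. The tie-break also has its own markers and needs no second selector.

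It can also be said that the Section 11 table is per dose level and never modelled selection between levels, and that weighing several markers against toxicity is a legitimate choice in a Phase Ib study. Both are fair. The first-stage column does not depend on which dose is expanded, and no printed figure is wrong. But the two-stage column and the 27% statement do assume LINE-1 passage before expansion, and a deliberate choice to weigh markers still has to be written so that it does not contradict the rule beside it.

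A reader might infer that the trial can expand a dose that failed its primary endpoint. The documents do not support that wording: the endpoint is to determine the BED, so what a level can miss is the LINE-1 definition. Nor does any section say that such a level will be expanded; the text only leaves it open.

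A reader might also note that the gate stops a 27% level with probability .798 (3 of 6) or .487 (2 of 6), and infer a similar rise in wrong declarations. That leaves out the final 7-of-16 cut.

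**Conclusion.** The conflict is real and bears on how the primary objective is answered. As written, the 10 expansion patients could be treated at a level that did not meet the BED definition, and the two-stage probabilities in Section 11 would not describe that path.

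The effect on error is small: at a true rate of 27%, .102 with the 2-of-6 gate against .112 without it, given expansion. The main cost is expansion patients spent on a dose that does not answer the primary question. These figures assume that the 7-of-16 cut still applies to a panel-chosen dose, that the first 6 patients are pooled with the 10, and that the panel's choice is unrelated to the LINE-1 count. The documents do not settle these points for the panel route.

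The mismatch between the 50% definition and the 2-of-6 cut is a separate issue.

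**What to change.** Reconcile Sections 6.3.1 and 11 with Sections 3.1 and 6.1.2. In both places, replace the panel sentence with text to this effect: the marker panel and adverse event profile are used only to choose among dose levels that have met the LINE-1 BED definition and the DLT rule; a level that has not met the LINE-1 definition is not expanded as the BED; all other markers are exploratory.

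Name the markers used for that choice, for example the HLA Class I/II APM and CD8+ measures already in the tie-break. State the order of precedence if the marker and adverse event rankings point to different levels. The text should refer to a single first-stage threshold, once the separate question of 3 of 6 or 2 of 6 is settled.

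This costs a few sentences in two sections, with no extra patients or procedures. The downside is that investigators lose the discretion to expand a dose on markers other than LINE-1. If they want to keep it, the panel, its thresholds and its decision rule need to be specified in advance and the Section 11 probabilities recomputed for that rule.

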Drug Substance Azacitidine/Decitabine (ASTX727)

Study Code 15-11430

Edition Number 13.0

Date 09202024

decatibine (ASTX727) will be administered alone in Cycle 1 and the combination of oral decatibine (ASTX727) and durvalumab therapy will be administered in Cycles 2-12 or until confirmed PD, initiation of alternative cancer therapy, unacceptable toxicity, withdrawal of consent, or another discontinuation criterion is met, whichever occurs first. The BED will be assessed on pre-treatment and post-treatment biopsies obtained at week 8. BED is defined as the dose of oral decatibine (ASTX727) that results in at least a 10% decrease in LINE-1 methylation from the baseline biopsy sample to the 8-week on-treatment tumor biopsy sample in at least 50% of patients treated within the same dose level. Accrual will be suspended until review of the LINE-1 methylation level in tissue from baseline and 8 weeks post baseline has been completed from patients entered into the first 2 dose levels (oral decitabine on Days 1-3 alone and Days 1-4 in a 4-week cycle). If the BED has not been determined in the first 2 dose levels and it is safe to do so, then the study will re-open to accrual and a subsequent group of 3 patients will receive the 3^{rd} dose level. If both the first 2 dose levels result in > 10% decrease in LINE-1 methylation, then the dose which induces the greatest fold change in HLA Class I/II APM expression and/or CD8+ T cell infiltration and with the lowest AE profile will be the dose utilized for the dose expansion group. Once the BED is determined, dose escalation will stop and the BED will be used in the expansion cohort. Dose Limiting Toxicity (DLT) will be assessed through 28 days post Cycle 2.

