3.2 Study schema

Figure 1. Study Flow Chart

Patients with recurrent or metastatic SCCHN who have progressed after to atment with an immunotherapy for recurrent or metastatic disease Durvalumab +/- tremelimumab +
dose escalation of DNA
methyltrasnferas inhibitor
(refer to charts below)

Progression Free Survival Objective Response Rate Overall Survival Biomarkers

Cohort (# of pts)	Azacitidine (28-day cycle)	Grade 3 or higher	2-fold DNMT1 inhibition in ≥50% of patients
D-1 (6)	20 mg/m2 on Days 1-5	MTD ²	BED ³
1 (6)	40 mg/m2 on Days 1-5	MTD ²	BED ³

Drug Substance Azacitidine/Decitabine (ASTX727)

Study Code 15-11430

Edition Number 13.0

Date 09202024

2 (6)	40 mg/m2 on Days 1-5 and 8-12	MTD ²	BED ³
3 (6)	75 mg/m2 on Days 1-5	MTD ²	BED ³

¹Azacitidine will be given starting Cycle 1 and durvalumab and tremelimumab will be given starting Cycle 2

³BED (biologically effective dose)

Cohort (# of pts)	Oral Decitabine (ASTX727) (28-day cycle)	Grade 3 or higher	10% decrease in LINE-1 methylation in ≥50% of patients
BD-1 (6)	ASTX727 one tablet on Days 1-2	MTD ²	BED ³
B1 (6)	ASTX727 one tablet on Days 1-3	MTD ²	BED ³
B2 (6)	ASTX727 one tablet on Days 1-4	MTD ²	BED ³
B3 (6)	ASTX727 one tablet on Days 1-5	MTD ²	BED ³

¹Oral decitabine (ASTX727) will be given starting Cycle 1 and durvalumab will be given starting Cycle 2

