6.3 Dose Escalation Decision Rules

Dose escalation monitoring

In order to ensure that patients are receiving the assigned dose of drug, oral decitabine (ASTX727), several measures will be employed.

Printed orders will be available.

The principal investigator, research nurse, and data manager will review the available toxicity data prior to continuing to escalate the dose and enrolling patients into the new cohort.

Prior to the start of each new dose level (i.e. accrual of a new cohort), a dated letter will be sent to the pharmacy which describes the change in dose.

Stopping rules

Dose escalations will continue until one of the following stopping rules has been satisfied:

- 1. The BED has been determined.
- 2.If at any time during accrual to a cohort, 2 or more patients in a dose cohort experience DLT, enrollment to that dose cohort will be terminated and dose escalation will stop.
- 3. Two of six patients treated at a reduced dose of oral decitabine (ASTX727) on Days 1-2 of a 28 day cycle experience a DLT

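### The BED is defined at 50% of patients in a dose level, but Section 11 computes its probabilities at 2 of 6 (33%) and 7 of 16 (44%)

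*Combined protocol and SAP*

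**What the plan says.** The definition is a share of patients at a dose level, and the share is 50% wherever it governs oral decitabine:

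- Section 3.1, repeated in 6.2: "8-week on-treatment tumor biopsy sample in at least 50% of patients treated within the same dose level".
- Section 3.2, schema: "10% decrease in LINE-1 methylation in ≥50% of patients".
- Section 6.3.1: "in at least 50% of patients treated within a dose level".
- Section 11, paragraph on the primary objective: "in at least 50% of patients treated within the same dose level".

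The stopping rules in Section 6.3 ("Dose escalations will continue until one of the following stopping rules has been satisfied") list determination of the BED first and give no count of their own. Section 11 adds that escalation then stops and that dose goes into the expansion cohort.

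The text introducing the Section 11 table says "BED is defined as outlined above". The table then gives the "probabilities of observing at least 33% of patients within a dose level with the BED for the first 6 patients", with a first column for at least 2 of 6 and a last column headed "Probability of ≥7 out of 16 meet BED definition". The stated values at true rates of 50/55/60% are .89/.93/.96 and .73/.84/.92. The text adds that a dose with a true rate of 27% would be used as the BED with probability 10%.

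**The concern.** Half of 6 is 3 and half of 16 is 8. A dose level with 2 of 6, or with 7 of 16 overall, counts as a success in the table and fails the definition. Neither cut-point appears in the definition or the stopping rules, and nothing says that 50% is a target true rate to be judged by lower observed counts. Outside the table, the pooled 16 patients have no criterion at all: Section 11 says only that the expansion is meant to show the BED rate is acceptable.

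Two things are at stake. First, the only operating characteristics offered for the primary objective belong to a looser rule than the one written. Second, conduct can differ. If neither of the first two levels reaches 3 of 6 and at least one has exactly 2 of 6, the definition says the BED has not been found and level 3 opens if safe. The Section 11 cut-point says the dose goes forward.

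**Working it through.** **Inputs (Section 11).** 6 evaluable patients per dose level, 10 more in the expansion, 16 pooled; true rates 50%, 55%, 60% and 27%; cut-points 2/6 and 7/16. The alternative first-stage cut-point of 3/6 follows from the 50% definition.

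**Formulae.** Let X ~ Bin(6, p) be responders in the first cohort and Y ~ Bin(10, p) responders in the expansion.

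- Stage 1: P(X ≥ a).
- Declared after expansion: P(X ≥ a and X+Y ≥ r) = Σ over x = a..6 of P(X = x) · P(Y ≥ r − x).

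**Step 1: reproduce the plan (a = 2, r = 7).** At p = .50, P(X ≥ 2) = 1 − (1 + 6)/64 = .891. The joint probability is .2344×.6230 + .3125×.8281 + .2344×.9453 + .0938×.9893 + .0156×.9990 = .735. The other true rates are computed in the same way.

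| True rate | Stage 1, ≥2/6 (stated) | Joint, ≥2/6 and ≥7/16 (stated) |
|---|---|---|
| 50% | .891 (.89) | .735 (.73) |
| 55% | .931 (.93) | .843 (.84) |
| 60% | .959 (.96) | .917 (.92) |
| 27% | – | .102 (10%) |

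All seven stated figures are recovered. To four decimals the joint value at 50% is .7347, which rounds to .73. The arithmetic is therefore sound for the looser cut-points.

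The last column is headed as conditional on at least 2 of 6, but its values are joint. Dividing joint by stage 1 gives the conditional values .82/.91/.96.

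**Step 2: apply the written definition (a = 3).** At p = .50, P(X ≥ 3) = 1 − (1 + 6 + 15)/64 = .656. The plan gives no pooled criterion in words, so both candidates are shown.

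| True rate | Stage 1, ≥3/6 | Joint, ≥3/6 and ≥8/16 | Joint, ≥3/6 and ≥7/16 |
|---|---|---|---|
| 50% | .656 | .493 | .589 |
| 55% | .745 | .633 | .706 |
| 60% | .821 | .755 | .802 |
| 27% | .202 | .031 | .070 |

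With the same 6 + 10 patients, the plan's .73 is reached only at a true rate of about 59% (with 8/16) or 56% (with 7/16).

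**Step 3: effect on opening level 3.** Assume that both first levels share one true rate. Level 3 opens, when safe, only if both cohorts miss the cut-point.

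- p = .50: under 3/6, P(X ≤ 2)² = .344² = .118; under 2/6, P(X ≤ 1)² = .109² = .012. The rules disagree in .118 − .012 = .106 of trials.
- p = .40: .544² = .296 against .233² = .054. They disagree in .242 of trials.

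**The case against.** The best defence is that the table has the usual layout for a target true rate judged by lower observed cut-points. Its rows are true rates starting at exactly 50%, the text calls 2/6 and 7/16 cut-points, and an error rate is given at 27%. There is a practical reason for such a design: an observed 50% requirement often rejects a dose whose true rate is 50%. This may well be what was intended. It is not written down, however. The definition is framed as a share of the patients treated, and Section 11 says the same definition applies.

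A second argument is that only the 50% definition governs escalation, with the table a loose planning calculation. It is true that no text outside the table says 2 of 6 stops escalation. But Section 11 passes a dose through the 2/6 gate to compute the probability that it is declared and used as the BED, so the table describes a dose-selection rule at odds with the definition.

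Third, Sections 6.3.1 and 11 call the LINE-1 criterion a working rule beside a marker panel. That softens the consequence, but supplies no other response-rate threshold. Levels 1 and 2 both enrol before the BED review, so the escalation effect is confined to level 3.

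The level-3 percentages are illustrations: they rest on a common true rate, and the 40% rate is not in the plan.

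**Conclusion.** The concern holds. The defect is a mismatch between definition and cut-points, not an arithmetic error. At a true rate of 50%, the written rule lowers the first-cohort probability by .23 (.89 to .66). It lowers the declaration probability by .24 with 8/16 (.73 to .49) or .14 with 7/16 (.73 to .59). It also makes acceptance of a dose with a true rate of 27% less likely: 3% or 7% instead of 10%. The two rules would disagree about opening level 3 in about 11% of trials if both levels have a true rate of 50%, and in about 24% at 40%.

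These figures assume independent patients and exactly 6 + 10 evaluable patients at the dose. This must be fixed, because the threshold decides the primary objective and currently has two values.

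**What to change.** Choose one rule and state it identically in Sections 3.1, 3.2, 6.2, 6.3.1 and 11.

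- **Option (a), keep 50%.** State 3 of 6 for determining the BED, state the pooled criterion (8 of 16 or 7 of 16), and replace the table and the 27% figure with the matching values above. The cost is a recalculated table and acceptance that declaration at a true 50% falls to .49 or .59. Restoring .73 at that rate would need more patients or a different design.
- **Option (b), keep the cut-points.** State that 50% is the target true rate, and that 2 of 6 determines and 7 of 16 confirms the BED. The table stands and the cost is wording only.

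Under either option, head the last column as the joint probability of passing both stages.

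Reconcile three related places at the same time:

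- The Table 5a footnote requires more than 50%, which read strictly means 4 of 6.
- Section 6.1.2 can be read as expanding the BED group to 10 patients rather than adding 10.
- Sections 3.1, 6.2 and one paragraph of 11 give level 3 only 3 patients, where Section 6.1.2 and later text in 11 give 6.

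The 6 + 10 calculations apply to level 3 only if it enrols 6.
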